1.0 PROTOCOL SUMMARY AND/OR SCHEMA

Abbreviated Title	Phase II of Neoadjuvant Olaparib in Combination with Pembrolizumab in Patients with Triple Negative Breast Cancer (TNBC) or Hormone Receptor-positive HER2-negative Breast Cancer And Germline Mutations in DNA Damage Repair Genes
Trial Phase	II
Clinical Indication	Neoadjuvant Breast Cancer/Germline mutations in DNA damage genes
Trial Type	Interventional
Type of control	Historical
Route of administration	Intravenous or oral
Trial Blinding	Unblinded Open-label
Treatment Groups	Single arm study Olaparib 300 mg orally BID Pembrolizumab 400 mg intravenously q6weeks
Number of trial participants	23 patients will be enrolled.
Estimated enrollment period	~24 months
Estimated duration of trial	We estimate the trial will require approximately 32 months from the time the first subject signs the informed consent until the last subject's last study-related phone call or visit.
Duration of Participation	Each subject will participate in the trial from the time he/she signs the Informed Consent Form (ICF) until withdrawing consent, becoming lost-to-follow-up, or end of study.
Estimated average length of treatment per patient	Subjects may be on study for ~6-36 weeks.

Trial Schema

Note: Patients in groups 1 and 2 will continue pembrolizumab every 6 weeks after surgery for up to 1 year total

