12.0 CRITERIA FOR REMOVAL FROM STUDY

Patients will be removed from the study when any of the criteria listed below applies. The reason for removal from the study and the date the patient was removed must be documented in the Clinical Research Database system.

All patients who have received at least one dose of each study treatment will be assessable for safety of the combination therapy. Patients who discontinue the study

before receiving their first dose of the study treatments will not be evaluable for safety assessment and should be replaced. Patients whose treatment is interrupted or permanently discontinued due to an AE or clinically significant laboratory value must be followed until resolution or stabilization of the event. A dose delay >3 weeks from the date of the planned dose may require the patient to be discontinued from the study treatment.

Patients are evaluable if they have completed the 6-week assessment. Radiographic response is assessed at 6 and (for those continuing) 12 weeks. Biopsy-confirmation of disease status at 6 and 12 weeks will be conducted at the time of the 6 and (for those continuing) 12 week assessments. pCR/RCB is assessed at the time of surgery.

Patient may continue on study until one of the following criteria applies:

- Confirmed radiographic disease progression
- Intercurrent illness that prevents further administration of treatment
- Unacceptable adverse experiences
- The participant or participant's legally acceptable representative requests to discontinue study treatment
- Physician decides to withdraw a participant from the study treatment or from the study for a reason not listed here
- The participant has a confirmed positive serum pregnancy test
- The participant is lost to follow-up
- Inability of the participant to comply with the requirement of the protocol for treatment or evaluation.
- End of study, whichever occurs first.

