The primary endpoint is pathologic assessment of MRI biopsy after neoadjuvant combination olaparib-pembrolizumab therapy at 12 weeks. The primary efficacy endpoint will be evaluated following completion of neoadjuvant therapy with combination olaparib and pembrolizumab X 12 weeks. In the primary analysis, patients whose 12-week imaging assessment or biopsy is not available will be counted as failures in the primary endpoint.

Patients are evaluable for the primary efficacy analysis if they have completed the 6-week assessment. An exception to this includes the rare patients who progressed during the first 6 weeks. These patients will be included in the primary analyses as failures. Note that any patients with progression or who drop out of the study from week 6 to 12 will be counted as failures for primary 12 week endpoint. Also note that patients who require a switch to SOC chemotherapy/ pembrolizumab after the 6 weeks biopsy

will be considered failures for the primary endpoint. All patients are evaluable for the safety analyses.

All evaluable patients (groups 1-3) will be included in our primary analysis. The sample size for this study is calculated using a Simon two-stage minimax design comparing a null true imaging-based complete response rate of 50% vs 75%. Our null rate comes from published literature which reports pCR rates in the range of ~44-54% in patients receiving neoadjuvant cytotoxic chemotherapy and ~53-65% in patients receiving either neoadjuvant immunotherapy or a targeted agent like a PARPi^{59, 73, 74,75}. In the first stage, 14 patients will be accrued. If there are 7 or fewer responses, then the study will be stopped. If 8 or more responses are observed, an additional 9 patients will be accrued for a total of 23 patients. If 16 or more responses are observed in 23 patients, the study regimen will be deemed successful. If 15 or fewer responses are observed, the study will be deemed unsuccessful. This design has a one-sided type I error rate of 0.05 and power of 0.80. The probability of stopping the study under the null is 0.60. At the end of the study, the image-guided biopsy CR rate will be calculated with a 95% confidence interval.

Up to 23 evaluable patients will be enrolled on this study. We anticipate enrolling 1-2 patients per month.

Secondary endpoints

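### The evaluability rule removes treated, non-progressing patients who miss the 6-week assessment from the primary analysis, contradicts the missing-equals-failure rule beside it, and leaves their replacement unstated

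*Combined protocol and SAP*

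**What the plan says.** **Who is analysed.** Section 14.0 (Sample size) says: "Patients are evaluable for the primary efficacy analysis if they have completed the 6-week assessment". The opening of Section 14.0 has the same condition, and Section 12.0 repeats it: "Patients are evaluable if they have completed the 6-week assessment". Section 14.0 then limits the primary analysis to evaluable patients in groups 1 to 3, and those groups are defined by tumour change on the 6-week MRI.

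**Who counts as a failure.** Section 14.0 (Sample size) lists:
- patients who progress before week 6, the one stated exception to the evaluability rule (Section 12.0 does not carry it);
- patients who progress or drop out between weeks 6 and 12;
- patients who switch to standard chemotherapy after the 6-week biopsy;
- in the paragraph just before the evaluability rule, patients for whom the 12-week imaging or biopsy is not available.

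**How many patients.** Section 1.0 says "23 patients will be enrolled". Section 14.0 says "Up to 23 evaluable patients will be enrolled on this study". The only replacement rule, in Section 12.0, concerns patients who leave "before receiving their first dose of the study treatments will not be evaluable for safety assessment and should be replaced".

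**Design.** A Simon two-stage minimax design, "comparing a null true imaging-based complete response rate of 50% vs 75" (percent). "In the first stage, 14 patients will be accrued"; the trial stops at 7 or fewer responses. Otherwise 9 more are accrued, and 16 or more responses in 23 is success. Stated properties are one-sided type I error 0.05, power 0.80 and probability 0.60 of stopping under the null.

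**The concern.** A treated patient who withdraws, dies without progression, is lost, or is taken off study for toxicity before the 6-week assessment has no negative 12-week biopsy. Under the evaluability rule that patient is in neither the numerator nor the denominator. The same event a few weeks later is a failure. The plan gives no reason for the difference.

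Membership of the analysis set then depends on how patients fared after starting treatment. If those who leave are non-successes, which is how the plan itself treats dropouts in weeks 6 to 12, their removal pushes the rate up against a fixed historical 50%. The trial is single-arm and open-label with a threshold of 16 in 23, so one or two patients matter. Because two sentences in one section give opposite answers, the denominator could also be settled after the results are visible.

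**Working it through.** **Inputs.** From Section 14.0: n1 = 14, stop at 7 or fewer; n = 23, success at 16 or more; p0 = 0.50, p1 = 0.75. Let d be the share of treated patients who miss the 6-week assessment without progression. The documents give no value for d, so it is an assumption and is varied. Excluded patients are taken to be non-successes.

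**Step 1: the plan's own figures.**
P(stop) = P(Bin(14, p) ≤ 7).
P(success) = Σ over x = 8 to 14 of P(Bin(14, p) = x) × P(Bin(9, p) ≥ 16 − x).
- p = 0.50: P(stop) = 0.605, P(success) = 0.0462.
- p = 0.75: P(success) = 0.8016.

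A search over two-stage designs with alpha ≤ 0.05 and power ≥ 0.80 also returns 7/14, 15/23 as the minimax design. The stated figures are correct for 23 patients who form the whole analysis set.

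**Step 2: excluded patients are replaced, up to 23 evaluable.** If the all-treated rate is 0.50, the rate among evaluable patients is 0.50/(1 − d). Putting this into the Step 1 formulas:

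| Excluded | Evaluable rate | P(stop at stage 1) | P(declare success) |
|---|---|---|---|
| none | 0.500 | 0.605 | 0.046 |
| 1 of 24 treated | 0.50 × 24/23 = 0.522 | 0.540 | 0.070 |
| 2 of 25 treated | 0.50 × 25/23 = 0.543 | 0.474 | 0.103 |
| 3 of 26 treated | 0.50 × 26/23 = 0.565 | 0.408 | 0.145 |
| d = 5% | 0.50/0.95 = 0.526 | 0.526 | 0.076 |
| d = 10% | 0.50/0.90 = 0.556 | 0.437 | 0.125 |
| d = 15% | 0.50/0.85 = 0.588 | 0.341 | 0.202 |

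The probability passes 0.05 at d of about 0.8%, which is less than one patient in 23.

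**Step 3: excluded patients are not replaced, and the cut-off stays at 16.** The result depends on what 75% refers to.
- *75% is the rate among evaluable patients.* P(Bin(22, 0.75) ≥ 16) = 0.70; with 21 evaluable, 0.57; with 20, 0.41. Alpha at an evaluable rate of 50% falls to 0.026, 0.013 and 0.006. With 22 or fewer evaluable patients, reaching 16 already implies at least 8 in the first 14, so the stage 1 rule does not change these figures.
- *75% is the all-treated rate and those excluded are non-successes.* They add nothing to the count whether included or not, so the chance of reaching 16 stays at about 0.80. Only the estimate moves: 16 successes are reported as 16/22 = 72.7% instead of 16/23 = 69.6%, and the interval shifts with it.

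**Step 4: all treated patients analysed, missing counted as failure, N = 23.**
- 50% and 75% as all-treated rates: alpha 0.0462, power 0.8016, as in Step 1.
- 75% as the rate among patients reaching week 6: the all-treated rate is 0.75 × (1 − d). At d = 5% this is 0.7125 and power is 0.67; at d = 10%, 0.675 and 0.51; at d = 15%, 0.6375 and 0.36.

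**The case against.** The strongest reply is that the plan already solves the problem: its sentence on unavailable 12-week results, read alone, covers a patient who left in week 3. That reading is possible. But the following paragraph restricts the analysis to patients with a 6-week assessment and makes a special exception for early progression, which would be unnecessary if every missing 12-week result already counted. The two sentences remain in conflict.

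Several stronger readings are tempting and should be set aside.
- *Anyone who stops drug for toxicity before week 6 is dropped.* Evaluability rests on the assessment, not on continued dosing. A patient who stops early but has the 6-week assessment stays evaluable and, without a negative 12-week biopsy, is a failure. Section 11.3.1 also allows olaparib interruptions, so early toxicity need not end participation.
- *Refusing the 6-week biopsy makes a patient non-evaluable.* Section 4.2 uses the 6-week assessment for tumour-size change, and Section 12.0 describes the biopsy as done alongside it. Nothing says that refusal of the biopsy alone excludes anyone.
- *Power is lost whenever excluded patients are not replaced.* Step 3 shows that this needs 75% to be the evaluable-only rate.
- *The design has no denominator at all.* Section 14.0 does name 23 evaluable patients. What is missing is agreement with Section 1.0 and a rule for treated, non-evaluable patients.

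It is also fair that the stated 5% holds within 23 evaluable patients, and that the exclusion rates used here are assumed.

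**Conclusion.** The point stands in this limited form. Followed as written, the evaluability rule removes treated, non-progressing patients who miss the 6-week assessment and biases the primary rate upward if they are non-successes. It conflicts with another sentence in the same section, and replacement of these patients is left open.

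With replacement, a single such patient among 24 treated takes the chance of a false success from 0.046 to 0.070, and two among 25 take it to 0.103, at a true all-treated rate of 50%. Without replacement, the certain effect is an inflated estimate and interval; a fall in power to 0.70 or 0.57 (one or two excluded) applies only if 75% describes evaluable patients. All of this assumes that excluded patients are non-successes. If no treated patient misses the 6-week assessment without progression, nothing changes. The sample-size arithmetic is not in question.

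**What to change.** In Sections 12.0 and 14.0:
- define the primary analysis set as all patients who received study treatment;
- count every patient without a negative 12-week biopsy as a failure, whatever the reason, including a missed 6-week assessment. This brings the evaluability rule into line with the existing sentence on unavailable 12-week results;
- apply 14 and 23, and the cut-offs 8 and 16, to treated patients, so that only undosed patients are replaced;
- state that 50% and 75% are all-treated rates;
- keep the rate among patients with a 6-week assessment as a sensitivity analysis.

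Make Sections 1.0 and 14.0 agree on 23 treated patients.

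**Cost.** No new data or procedures. The reported rate will be slightly less favourable if there are early losses. If the sponsor meant 75% for patients reaching week 6, this is more than a wording change: power at 23 patients must be restated (0.67 at 5% and 0.51 at 10% early loss) and the sample size reconsidered.

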the ability to predict pathologic complete response of breast cancer in the neoadjuvant setting.

Preliminary data pertinent to the below described study design is the proof-of-concept clinical trial (NCT03289195) lead by co-investigator [name] that evaluated the accuracy of MRI-guided biopsy for diagnosing a post-NAC pCR compared with reference-standard surgical resection. This was single-arm, single-institution, phase 1 study from September 2017–July 2019. The median follow-up was 1.26 years (interquartile range, 0.85–1.59). Data analysis was performed in November 2019. Patients had stage 1A–3C biopsy-proven operable invasive breast cancer; standard-of-care NAC; pre- and post-NAC MRI with imaging complete response defined as no residual enhancement on post-NAC MRI; and definitive surgery. Post-NAC MRI-guided biopsy without the use of intravenous contrast of the tumor bed prior to definitive surgery. The primary endpoint was the negative predictive value (NPV) of MRI-guided biopsy, with true negative defined as a negative biopsy (i.e. no residual cancer) that corresponded with a surgical pCR. Accuracy, sensitivity, positive predictive value (PPV) and specificity were also calculated. 20 patients were evaluable (100% female; median age, 51.5 years); 19/20 (95%) had invasive ductal carcinoma; 15/20 (75%) had stage 2 cancer; 11/20 (55%) had HER2 positive cancer; and 6/20 (30%) had triple negative cancer. Surgical pathology demonstrated a pCR in 13/20 (65%) patients and no-pCR in 7/20 (35%) patients, with pCR was defined as no residual invasive cancer. MRI-guided biopsy had an NPV of 92.8%, with accuracy, sensitivity, PPV, and specificity of 95%, 85.8%, 100%, and 100%, respectively. Only 1 patient had a false negative MRI-guided biopsy for which surgical pathology demonstrated less than 0.02 cm of residual invasive cancer. The accuracy of MRI-guided biopsy to diagnose a post-NAC pCR approaches that of reference-standard surgical resection. MRI-guided biopsy may be a viable alternative to surgical resection for this population following NAC.

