4.0 OVERVIEW OF STUDY DESIGN/INTERVENTION

4.1 Design

This trial is designed as a single-arm, open-label, non-randomized study with sample size calculated using the Simon two-stage minimax design. The primary endpoint is pathologically negative MRI-guided biopsy after neoadjuvant combination olaparib-pembrolizumab therapy at 12 weeks. Patients are eligible if they have newly diagnosed cT1c-3N0-3M0 invasive breast cancer, either triple negative according to ASCO/CAP guidelines or hormone receptor positive breast cancer with a germline mutation in BRCA1, BRCA2, PALB2, RAD51C, or RAD51D and have undergone a pre-neoadjuvant chemotherapy MRI.

At baseline, consented patients will undergo a research tumor biopsy and the index tumor volume will be quantified on the standard of care breast MRI. Patients will then receive olaparib and pembrolizumab for 6-12 weeks, followed by SOC chemotherapy +/- pembrolizumab and surgery. Depending on response to study therapy, the sequence of cytotoxic chemotherapy +/- pembrolizumab vs surgery will be determined by the primary clinical team. At the 6-week timepoint, all patients will undergo MRI for tumor assessment of interval response, which will be immediately followed by a concurrent MRI-guided biopsy. Similarly, at the 12-week timepoint, all patients who remain on olaparib/pembrolizumab for > 6 weeks will undergo another MRI for tumor assessment of interval response, which will be immediately followed by a concurrent MRI-guided biopsy.

At 6 weeks of treatment, the first study MRI will be performed, and treatment response will be assessed by comparing difference in tumor volume on this MRI to that measured on the pre-neoadjuvant chemotherapy MRI. Patients will be categorized as follows:

Group 1: Decrease in tumor volume

- 1a) Decrease in tumor volume of at least 50% ($\geq 50\%D$)
- 1b) Decrease in tumor volume of 0 to 50% ($< 50\%D$)

Group 2: Enlargement in tumor volume of 0 to 25% ($< 25\%E$)

Group 3: Enlargement in tumor volume of 25% or greater

All evaluable patients across the 4 categories will be included for the primary endpoint.

Patients who are responding (any decrease in tumor size, groups 1a and 1b above) will continue the study therapy for 6 additional weeks after the initial tumor

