14.0 BIOSTATISTICS

This trial is designed as a single-arm, open-label, non-randomized study with sample size calculated using the Simon two-stage minimax design. The primary endpoint is pathologically negative MRI-guided biopsy after neoadjuvant combination olaparib-pembrolizumab therapy at 12 weeks. Patients are eligible for this study if they have newly diagnosed high-risk early-stage invasive breast cancer, either triple negative according to ASCO/CAP guidelines or hormone receptor positive breast cancer with a germline mutation in BRCA1, BRCA2, PALB2, RAD51C, or RAD51D. As noted in section 3.6, our preliminary work suggests that MRI-guided biopsy has high specificity

and sensitivity in diagnosing pCR compared with the reference of standard surgical pathology.

At the 6 week timepoint, patients will be categorized as follows:

Group 1: Decrease in tumor size

1a) Decrease in tumor size of at least 50% ($\geq 50\%D$)

1b) Decrease in tumor size at 6-weeks of 0 to 50% ($< 50\%D$)

Group 2: Enlargement in tumor size of 0 to 25% ($< 25\%E$)

Group 3: Enlargement in tumor size of 25% or greater

All evaluable patients across the 4 categories will be included for the primary endpoint.

Patients who are responding (any decrease in tumor size, groups 1a and 1b above) will continue the study therapy for another 6 weeks. Patients who have increases in tumor size of 0-25% (group 2) at the 6-week timepoint can continue study therapy for another 6 weeks or elect SoC chemotherapy/pembrolizumab vs surgery. To ensure safety, patients who have a $> 25\%$ increase in tumor size from the preceding imaging at any point (group 3) will immediately move to SoC chemotherapy vs surgery. For all 4 groups following completion of the study therapy, conventional treatment will commence. These group delineations are outlined in details because this determines how patients will be treated on study.

All patients who have received at least one dose of each study treatment will be assessable for safety of the combination therapy. Patients are evaluable for the primary endpoint if they have completed the 6-week assessment. Biopsy-confirmed radiographic complete response will be determined at the 12-week timepoint. pCR/RCB0 will be determined at the time of surgery.

Sample size

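### Section 14 states its hypotheses on an imaging response and takes the 50% null from surgical pCR, while the named primary endpoint is a negative 12-week biopsy, so the 5% error is not established against the pCR benchmark.

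*Combined protocol and SAP*

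**What the plan says.** Section 4.1 states: "The primary endpoint is pathologically negative MRI-guided biopsy after neoadjuvant combination olaparib-pembrolizumab therapy at 12 weeks". The primary objective in Section 2.0 and the opening of Section 14.0 agree, and the sample-size text calls the endpoint a pathologic assessment of the MRI biopsy. None of these places attaches an imaging condition.

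Section 14.0 then uses other terms. It says "Biopsy-confirmed radiographic complete response will be determined at the 12-week timepoint". It sets the hypotheses by "comparing a null true imaging-based complete response rate of 50% vs 75" (per cent). The quantity to be estimated at the end of the study is called an image-guided biopsy CR rate.

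On the source of the null, Section 14.0 says "Our null rate comes from published literature which reports pCR rates in the range of ~44-54" (per cent) with cytotoxic chemotherapy, and about 53-65% with immunotherapy or a targeted agent. Sections 11.0 and 13.2 define pCR on the surgical specimen: no residual invasive cancer in the breast and no nodal metastasis, DCIS allowed.

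The link from biopsy to pCR is the pilot in Section 3.6. It had 20 evaluable patients and required "pre- and post-NAC MRI with imaging complete response defined as no residual enhancement on post-NAC MRI". Its result was: "MRI-guided biopsy had an NPV of 92.8%, with accuracy, sensitivity, PPV, and specificity of 95%, 85.8%, 100%, and 100%, respectively".

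The decision rule begins "In the first stage, 14 patients will be accrued. If there are 7 or fewer responses, then the study will be stopped". Otherwise accrual continues to 23 patients, and 16 or more responses is success. The plan adds: "This design has a one-sided type I error rate of 0.05 and power of 0.80".

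**The concern.** Biopsy result and imaging complete response are not synonyms in this protocol. Section 13.3 defines imaging response separately, a secondary objective studies its association with the biopsy result, and Section 14.0 compares the two by McNemar's test. The terms therefore classify some patients differently:

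| 12-week finding | Negative biopsy (named endpoint) | Biopsy-confirmed radiographic CR | Imaging-based CR |
|---|---|---|---|
| Biopsy negative, residual enhancement | success | failure | failure |
| Biopsy positive, imaging CR | failure | failure | success |

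The go/no-go decision is one count against one historical null, and one reclassified patient can move it across 7/14 or 16/23. If the reading is settled only after the data are seen, the result can depend on the choice.

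The null raises a second question. The 50% describes surgical pCR, while the count is of negative needle biopsies of the breast. If the two rates differ in patients whose pCR rate is 50%, a regimen no better than the benchmark passes with a probability other than the stated 0.05.

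**Working it through.** **Step 1: reproduce the plan's figures.** Inputs from Section 14.0: n1 = 14, stop at 7 or fewer; n = 23, success at 16 or more.

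P(success | p) = sum over x = 8 to 14 of P[Bin(14, p) = x] × P[Bin(9, p) ≥ 16 − x].

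- p = 0.50: P(success) = 0.0462 and P(early stop) = 0.6047. The plan states 0.05 and 0.60.
- p = 0.75: P(success) = 0.8016. The plan states 0.80.

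A full search confirms this as the minimax design for these inputs. The calculation uses only p, so it is valid for any binary endpoint whose null rate really is 50%.

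**Step 2: rebuild the pilot table.** Section 3.6 gives 13 pCR, 7 without pCR, one false negative and 100% specificity. So 6 of 7 residual cancers were detected and 13 of 14 negative biopsies were correct. Sensitivity for residual cancer is 6/7, the miss rate is 1/7, and NPV is 13/14, matching the published figures to rounding. The exact 95% interval for 6/7 is 42% to 99.6%.

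**Step 3: carry a 50% pCR rate over to the biopsy scale.** With specificity 100%, as in the pilot:

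biopsy-negative rate = pCR + (1 − pCR) × (1 − sensitivity).

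At pCR = 0.50 and sensitivity 6/7 this is 0.50 + 0.50 × 1/7 = 0.571. Applying the unchanged rule:

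| Biopsy sensitivity | Biopsy-negative rate | P(success) |
|---|---|---|
| 100% | 50.0% | 0.046 |
| 99.6% (upper limit) | 50.2% | 0.048 |
| 95% (assumed) | 52.5% | 0.074 |
| 90% (assumed) | 55.0% | 0.114 |
| 6/7 (pilot) | 57.1% | 0.159 |
| 70% (assumed) | 65.0% | 0.411 |
| 42% (lower limit) | 78.9% | 0.91 |

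At the pilot value, early stopping falls from 0.60 to 0.39.

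**Step 4: factors in the other direction.** Step 3 assumes that clearance at week 12 equals the benchmark pCR rate and that every patient without pCR has a 12-week biopsy. Neither need hold.

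- Section 14.0 counts early progression, dropout between weeks 6 and 12, a switch to standard chemotherapy and a missing 12-week assessment as failures. If 40% of non-pCR patients fail this way (assumed), the rate is 0.50 + 0.50 × 0.60 × 1/7 = 54.3% and P(success) is 0.10. At 60% it is 52.9% and 0.08.
- The biopsy is read at 12 weeks; the benchmark pCR rates are read at surgery. If true clearance at week 12 were 42% (assumed) in place of 50%, the rate is 0.42 + 0.58 × 1/7 = 50.3% and P(success) is 0.049.

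**The case against.** The strongest reply is that there is one primary endpoint, loosely worded in places. Every sentence that says what the primary endpoint is names biopsy pathology, and the sentence on biopsy-confirmed radiographic response never calls that primary. This stands. A reader might infer three competing primary endpoints, but the documents show one named endpoint and mismatched terms around it. It does not remove the problem, because the sentence carrying the null and alternative rates is one of those mismatched.

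A second reply is that the stated error is correct. It is, for a biopsy-negative rate of 50%. What the plan lacks is a reason why 50% is the right null for that rate.

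A third reply is that the size of any inflation is not known. This also stands. The figure of 0.16 rests on one miss in seven patients, all selected for imaging complete response after standard chemotherapy. Sensitivity may differ where tumour is still visible. Leaving nodes unsampled makes a negative result easier than pCR; the factors in Step 4 make it harder. The plan does not say whether DCIS alone in the biopsy counts as negative.

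It is also tempting to conclude that success should require both a negative biopsy and imaging complete response. That would change the named endpoint, leave the null still borrowed from surgical pCR, and cost power. If 5% or 10% of biopsy-negative patients still enhance (assumed), a 75% biopsy-negative rate becomes 71.25% or 67.5%, and power falls from 0.80 to 0.67 or 0.51. Section 3.6 itself notes that imaging complete response after chemotherapy has no standard definition.

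**Conclusion.** The point holds on two counts. The hypothesis sentence is written on a measure other than the named primary endpoint. The 50% null belongs to a surgical breast-and-node result, so the stated 0.05 (exact 0.046) is not established against a 50% pCR benchmark.

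The size of the discrepancy cannot be fixed from the documents. Under Step 3's assumptions, P(success) at a 50% pCR rate is 0.074 at 95% sensitivity and about 0.16 at the pilot value, and it runs from 0.048 to 0.91 over the pilot interval. Plausible offsets bring it back to about 0.05. A reader might infer that the trial's true error is 16%, or that the 5% is miscalculated; the documents support neither.

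It still needs correcting before analysis, because the only efficacy decision is this one count against this one null.

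**What to change.** 1. In the hypothesis sentence of Section 14.0, replace the imaging-based term with 12-week biopsy-negative rate. Use that same term for the biopsy-confirmed radiographic response and for the rate estimated at the end of the study. Keep the primary endpoint as named in Sections 2.0 and 4.1.
2. State that the 5% error and 80% power refer to biopsy-negative rates of 50% and 75%. Add that 16 of 23 does not by itself show improvement over a 50% surgical pCR rate, and give the error over a range of biopsy sensitivities, as in the Step 3 table, with its assumptions. Do not enter 0.16 as the error rate.
3. Pre-specify the proportion with both a negative biopsy and imaging complete response at 12 weeks as a sensitivity analysis.

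The cost is protocol wording and slightly more analysis; the MRI and biopsy data are already collected. The downside is that the claim attached to the error rate becomes less favourable.
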